4.3. Study Termination

The investigator retains the right to terminate study participation at any time, according to the terms specified in the study contract. The investigator/head of the study site (Japan) is to notify the IRB/IEC in writing of the study's completion or early termination, send a copy of the notification to the sponsor or sponsor's designee, and retain 1 copy for the site study regulatory file.

The sponsor may terminate the study electively, if, for example, required by regulatory decision or upon advice of the DSMB. If the study is terminated prematurely, the sponsor will notify the investigators/head of the study site (Japan), the IRBs and IECs, and regulatory bodies of the decision and reason for termination of the study. The DSMB will recommend termination of the study if warranted, as described in Section 5.6. For Japan, the decision from the sponsor will be via the head of the study site(s) who will notify the investigators and the IRBs of the decision and reason for termination of the study.

5. STUDY POPULATION

Deviations from eligibility criteria are not allowed because they can potentially jeopardize the scientific integrity of the study, regulatory acceptability, and/or participant safety. Therefore, adherence to the criteria as specified in the Protocol is essential. Prospective approval of Protocol deviations to recruitment and enrollment criteria, also known as Protocol waivers or exemptions, are not permitted.

5.1. Inclusion Criteria

Participants are eligible to be included in the study only if all of the following criteria apply:

- 1. Ability to comprehend and willingness to sign a written ICF for the study.
- 2. Men or women, age \geq 18 years at the time of signing the ICF.
- 3. Diagnosis of primary wAIHA based on the presence of hemolytic anemia and serological evidence of anti-erythrocyte antibodies, detectable by a DAT positive for IgG only or IgG plus C3d.
 - *Note:* A DAT performed at screening is preferred; however, prior documentation of DAT results within 3 months of randomization is permitted.
- 4. Participants who were inadequately controlled with, were intolerant to, or have a contraindication to other therapies. There is no limit to the number of prior treatment regimens.
- 5. Hemoglobin \geq 6.5 to < 10 g/dL with symptoms of anemia as assessed by the investigator at screening (hemoglobin as determined by local laboratory).
- 6. FACIT-F score \leq 43 at screening.
- 7. Willingness to avoid pregnancy or fathering children based on the criteria below.
 - a. Male participants with reproductive potential must agree to take appropriate precautions to avoid fathering children (with 99% certainty) from screening through 90 days after the last dose of study drug and must refrain from donating sperm during this period. Permitted methods in that are at least 99% effective preventing pregnancy (see Appendix A) should be communicated to the participants and their understanding confirmed.
 - b. Female participants who are WOCBP must have a negative serum pregnancy test at screening and a negative urine pregnancy test before randomization and must agree to take appropriate precautions to avoid pregnancy (with 99% certainty) from screening through 90 days after the last dose of study drug and must refrain from donating oocytes during this period. Permitted methods that are at least 99% effective preventing pregnancy (see Appendix A) should be communicated to the participants and their understanding confirmed.
 - c. A female participant not considered to be of childbearing potential as defined in Appendix A is eligible.
 - *Note:* This criterion does not apply to women of nonchildbearing potential (i.e., surgically sterile with a hysterectomy and/or bilateral oophorectomy OR

- postmenopausal, defined as amenorrhea at least 12 months before screening, confirmed by FSH levels at screening).
- 8. Willingness to receive PJP prophylaxis during the study period from Day 1 through at least 2 to 6 months after the last dose of study drug.
- 9. For participants in France only: COVID-19 vaccination at least 2 weeks prior to randomization.
- 10. For participants in France only: Participant is up-to-date with mandatory vaccinations according to the national vaccination program as assessed by the investigator.

5.2. Exclusion Criteria

Participants are excluded from the study if any of the following criteria apply:

- 1. Women currently pregnant or breastfeeding or participants expecting to conceive or father children within the projected duration of the study, starting with the screening visit through 90 days from the date of last dose of study drug.
- 2. A diagnosis of other types of AIHA; CAD, cold agglutinin syndrome, mixed-type AIHA or paroxysmal cold hemoglobinuria.
- 3. Warm AIHA suspected to be secondary to a lymphoproliferative malignancy or secondary to an autoimmune disease (eg, systemic lupus erythematosus, Castleman's disease, Sjögren's syndrome, or other autoimmune diseases) or diagnosis of Evans syndrome.
- 4. A splenectomy less than 3 months before randomization.
- 5. Concurrent conditions or history of other diseases:
 - a. History or clinical manifestations of significant unstable metabolic, hepatic, renal, hematological, pulmonary, cardiovascular, gastrointestinal, urological, neurological, or psychiatric disorders.
 - b. Current or previous malignancy within 5 years of study entry, except basal or squamous cell skin cancer with removal considered to be curative, superficial bladder cancer, prostate intraepithelial neoplasm, carcinoma in situ of the cervix, or other noninvasive or indolent malignancy without sponsor approval.
 - c. Clinically significant cardiac disease, including unstable angina, acute myocardial infarction, and/or cardiac conduction issues within 6 months of randomization.
 - d. Current New York Heart Association Class II to IV congestive heart failure or uncontrolled arrhythmia.
- 6. Known diagnosis of anti-phospholipid syndrome or history of persistent anti-phospholipid antibodies.
 - *Note:* Participants at risk for thrombosis who are on adequate prophylaxis or those with thrombosis on stable treatment for 3 months prior to randomization are eligible.
- 7. Hepatitis B (HBV) or hepatitis C (HCV) infection: Participants who are positive for the hepatitis B surface antibody or hepatitis B core antibody will be eligible if they are negative for HBV-DNA; these participants should be considered for prophylactic

- antiviral therapy. Participants who are positive for the anti-HCV antibody will be eligible if they are negative for HCV-RNA.
- 8. Known HIV infection or positivity on immunoassay.
 - *Note:* HIV screening test is optional for participants enrolled in the United States, but participants with known HIV infection enrolled in the United States will be excluded.
- 9. History or presence of an abnormal ECG that, in the investigator's opinion, is clinically meaningful. Participants with screening QTc interval > 470 milliseconds for males and > 480 milliseconds for females (corrected by Fridericia) are excluded. In the event that a single QTcF is > 470 milliseconds for males or > 480 milliseconds for females, the participant may enroll if the average QTcF for triplicate ECGs is < 470 milliseconds for males or < 480 milliseconds for females.
- 10. Use of the following medications:
 - a. Treatment with rituximab within 6 weeks of randomization.
 - b. Use of immunosuppressive therapy within 28 days of the randomization. Immunosuppressive therapy includes, but is not limited to, cyclosporine A, azathioprine, mycophenolate mofetil, or cyclophosphamide.
 Note: Participants receiving corticosteroids must be at a stable dose level (no change in daily dose) ≤ 40 mg/day (prednisone or equivalent corticosteroid dose) for at least 14 days prior to randomization.
 - c. Use of IVIG or erythropoietin within 2 weeks of randomization.
 - d. Chronic or current active infectious disease requiring systemic antibiotics, antifungal, or antiviral treatment or exposure to a live vaccine within 30 days of randomization.
 - e. Use or expected use during the study of any prohibited medications (see Section 6.7.3), including potent CYP3A4 inhibitors or moderate or potent CYP3A4 inducers, within 14 days or 5 half-lives (whichever is longer) before randomization (see Appendix E).
- 11. Current treatment or treatment within 30 days or 5 half-lives (whichever is longer) before randomization with another investigational medication, or current enrollment in another investigational drug and/or device protocol.
- 12. Known hypersensitivity or severe reaction to parsaclisib or its excipients (IB).
- 13. Unable to swallow oral medication, malabsorption syndrome, disease significantly affecting gastrointestinal function, total resection of the stomach or small bowel, ulcerative colitis, symptomatic inflammatory bowel disease, or partial or complete bowel obstruction.
- 14. Current alcohol or drug use that, in the opinion of the investigator, will interfere with the participant's ability to comply with the dose regimen and study evaluations.
- 15. Participants who, in the opinion of the investigator, are unable or unlikely to comply with the dose regimen and study evaluations.
- 16. Any condition that would, in the investigator's judgment, interfere with full participation in the study, including administration of study drug and attending required study visits; pose a significant risk to the participant; or interfere with interpretation of study data.

- 17. Prior treatment with parsaclisib or another PI3Kδ, or a pan-PI3K inhibitor for any indication.
- 18. Participants with laboratory values at screening defined in Table 7.

Table 7: Exclusionary Laboratory Values

Lal	boratory Parameter ^a	Exclusion Criterion	
He	matology		
a	Platelets	$\leq 100 \times 10^9 / L$	
b	ANC	$\leq 1.5 \times 10^9/L$	
с	WBCs	$\leq 1.5 \times 10^9/L$	
He	patic		
d	ALT	≥ 2 × ULN	
e	AST	≥ 2 × ULN unless clearly related to active hemolysis	
Rei	Renal		
f	eGFR using 2021 CKD-EPI (Inker et al 2021)	≤ 45 mL/minute/1.73m ²	

^a If the central laboratory is unable to perform the test due to hemolysis related to wAIHA or the analytical method, then local laboratory test results may be used to determine participant eligibility.

5.3. Lifestyle Considerations

5.3.1. Meals and Dietary Restrictions

Parsaclisib/placebo will be taken orally with water without regard to food except on mornings of clinic visits. See Section 8.5 for details on further requirements before and after the start of

5.4. Screen Failures

Screen failures are defined as participants who consent to participate in the clinical study but are not subsequently randomly assigned to study treatment.

Individuals who do not meet the criteria for participation in this study (screen failure) may be rescreened.

Tests with results that fail eligibility requirements may be repeated during screening if the investigator believes the result to be in error. Additionally, a participant who fails screening may repeat the screening process if the investigator believes that there has been a change in eligibility status. Participants who rescreen must reconsent and be assigned a new participant number.

5.5. Replacement of Participants

No participants will be replaced at any time during this study. However, the COVID-19 global pandemic may present challenges to the normal conduct of this study and may require the outline of potential mitigation strategies described in Appendix B.

5.6. Data Safety Monitoring Board

This study will use an eDSMB to monitor safety as detailed in the DSMB charter.

The voting members of the committee are external to the sponsor. The members of the eDSMB will not be involved with the study in any other way (eg, they cannot be study investigators) and will have no competing interests that could affect their roles with respect to the study.

The eDSMB will make recommendations to the sponsor regarding steps to ensure both participant safety and the continued ethical integrity of the study. Specific details regarding composition, responsibilities, and governance, including the roles and responsibilities of the various members and the sponsor, IEC, and protocol team; and requirements for and proper documentation of eDSMB reports, minutes, and recommendations will be described in the eDSMB charter that is reviewed and approved by all eDSMB members.

6. STUDY TREATMENT

6.1. Study Treatments Administered

Information regarding study drug and study drug administration is provided in Table 8. Further information regarding study drug administration is provided in Appendix C. The COVID-19 global pandemic may present challenges to the normal conduct of this study, requiring the outline of potential mitigation strategies described in Appendix B.

Table 8: Study Treatment Information

Study treatment name:	Parsaclisib	Matching Placebo	
Mechanism of action:	PI3Kδ inhibitor	Not applicable	
Dosage formulation:	Tablet Matching Tablet		
Unit dose strength(s)/dosage level(s):	2.5 mg 1 mg	2.5 mg 1 mg	
Administration instructions:	1 tablet orally QD. Parsaclisib or matching placebo will be taken orally with water without regard to food except on mornings of clinic visits. Participants should not take their dose at home when they have a visit. Parsaclisib should be taken at approximately the same time each day.		
Packaging and labeling:	Parsaclisib and matching placebo will be packaged in high-density polyethylene bottles. No preparation is required. All Incyte investigational product labels will be in the local language and will comply with the legal requirements of each country.		
Storage:	Bottles of parsaclisib and matching placebo should be stored at ambient conditions (15°C-30°C or 59°F-86°F).		
Status of treatment in participating countries:	Investigational	Not applicable	

6.2. Preparation, Handling, and Accountability

The investigator, investigational drug storage manager (for Japan), or designee must confirm appropriate temperature conditions have been maintained during transit for all study treatments received and any discrepancies are reported and resolved before use of the study treatment.

Only participants enrolled in the study may receive study treatment, and only authorized site staff may supply or administer study treatment. All study treatment must be stored in a secure, environmentally controlled, and monitored (manual or automated) area in accordance with the labeled storage conditions with access limited to the investigator, investigational drug storage manager (for Japan), and authorized site staff.

The investigator, investigational drug storage manager (for Japan), or designee is responsible for study treatment accountability, reconciliation, and record maintenance (ie, receipt, reconciliation, and final disposition records). Inventory and accountability records must be maintained and readily available for inspection by the study monitor and are open to inspection at any time by

any applicable regulatory authorities. The investigator, investigational drug storage manager (for Japan) or designee must maintain records that document the following:

- Delivery of study drug to the study site.
- Inventory of study drug at the site.
- Participant use of the study drug, including tablet counts from each supply dispensed.
- Return of study drug to the investigator, investigational drug storage manager (for Japan) or designee by participants.

The investigational product must be used only in accordance with the Protocol (see Section 6). The investigator will also maintain records adequately documenting that the participants were provided the specified study drug. These records should include dates, quantities, and any available batch or serial numbers or unique code numbers assigned to the investigational product and study participants.

Completed accountability records will be archived by the site. The investigator, investigational drug storage manager (for Japan) or designee will be expected to collect and retain all used, unused, and partially used containers of study drug until verified by the study monitor (unless otherwise agreed to by the sponsor). At the conclusion of the study, the investigator, investigational drug storage manager (for Japan), or designee will oversee shipment of any remaining study drug back to the sponsor or its designee for destruction according to institutional SOPs. If local procedures mandate on-site destruction of the investigational supply, the site should (where local procedures allow) maintain the investigational supply until the study monitor inspects the accountability records in order to evaluate compliance and accuracy of accountability by the investigative site. At sites where the study drug is destroyed before monitor inspection, the monitors rely on documentation of destruction per the site SOP.

Further guidance and information for the final disposition of unused study treatments are provided in the Study Pharmacy Manual.

6.3. Measures to Minimize Bias: Randomization and Blinding

All participants will be centrally assigned to study treatment using an IRT (see Section 8.1.3). Before the study is initiated, the telephone number and call-in directions for the IRT and/or the log in information and directions for the IRT will be provided to each site. Full details will be provided in the IRT Study Reference Manual.

Study drug will be dispensed at the study visits summarized in the SoA (see Table 3 and Table 4). Returned study drug should not be redispensed to the participants.

Participants, investigators, and the sponsor will remain blinded to each participant's treatment assignment throughout the double-blind portion of the study. Emergency unblinding will occur if an AE requires the investigator to be made aware of the participant's treatment assignment (see emergency unblinding procedures in Section 9.7 and refer to the IRT Study Reference Manual).

6.4. Study Treatment Compliance

Compliance with all study-related treatments should be emphasized to the participant by the site personnel, and appropriate steps should be taken to optimize compliance during the study. Compliance with study drug will be calculated by the sponsor based on the drug accountability documented by the site staff and monitored by the sponsor/designee. Participants will be instructed to bring all unused study drugs with them to the study visits in order for site personnel to conduct to assess study drug accountability.

Compliance with study drug administration will be calculated by the sponsor based on study drug accountability records documented by the site staff and monitored by the sponsor/designee.

Participant compliance must be within 80% to 120%, assessed at each study visit. If compliance is outside of this range, it will be considered a protocol deviation. Participants consistently noncompliant with the study drug may be withdrawn from the study. The decision to withdraw a participant will be made by the investigator after consultation with the sponsor, and relevant correspondence will be archived in the site study file.

6.5. Dose Modifications

Dose modifications will be allowed during the study as defined in Section 6.5.1. In some circumstances, it may be necessary to temporarily interrupt treatment with study drug as a result of AEs or laboratory abnormalities that have an unclear relationship to the study drug.

6.5.1. Criteria and Procedures for Dose Interruptions and Adjustments of Study Drug

Safety concerns should be discussed with the sponsor immediately upon occurrence or awareness to determine if the participant should continue or discontinue study treatment.

Dose modifications are allowed in the study. Dose reductions from 2.5 mg QD to 1 mg QD are allowed after consultation with the medical monitor, if the participant is experiencing an AE assessed as related or of unknown relationship to study drug or for hemoglobin levels in the high end of normal range. Because participants may enter the study with extensive pretreatment and/or hemolysis associated with the primary disease, these dose reduction rules are provided as guidelines (see Table 9). Dose re-escalation is permitted provided the investigator consult with the sponsor medical monitor and the sponsor approves before dose re-escalation.

In some circumstances, it may be necessary to temporarily interrupt treatment with parsaclisib as a result of AEs or laboratory abnormalities that have an unclear relationship to the study drug (see Table 9). Except in cases of emergency, it is recommended that any laboratory findings be confirmed and that the investigator consult with the sponsor medical monitor (or other representative of the sponsor) before temporarily interrupting study drug. Participants who experienced a recurrence of the AEs or laboratory abnormalities upon restarting the study drug may have the study drug permanently discontinued (see Section 7.1.2).

During the study, study treatment may be delayed up to 21 days to allow for resolution of toxicity. Participants may resume treatment if no medical condition or other circumstance exists that, in the opinion of the investigator, would make the participant unsuitable for further participation in the study. The treating investigator should contact the sponsor to discuss the

case of any participant whose treatment has been delayed for more than 7 days before restarting study treatment. See Appendix D for action required for potential Hy's law cases.

Table 9: Guidelines for Interruption and Restarting of Study Drug

ADVERSE EVENT	ACTION TAKEN
Chemistry	
Grade 2 AST and/or ALT is > 3.0 - 5.0 × ULN	Step 1: Interrupt study drug up to 21 days and repeat ALT/AST assessments weekly for up to 3 weeks (local blood collection may be used) or until ALT and/or AST results are < 3.0 × ULN.
	Step 2: Restart study drug at the same dose and monitor as clinically indicated.
	• If ALT and/or AST result(s) do not decrease to < 3.0 × ULN after 3 weeks of drug interruption, discontinue study drug administration, and the participant will enter the post-treatment follow-up period.
	• If AST or ALT elevation > 3.0-5.0 × ULN reoccurs following restarting study medication administration, repeat Step 1 and then restart study drug at 1 mg QD dose.
	• If AST and ALT > 3.0-5.0 × ULN reoccurs on lower dose, discontinue study drug administration, and the participant will enter the post-treatment follow-up period.
≥ Grade 3 AST and/or ALT is > 5.0 × ULN	Step 1: Interrupt study drug up to 21 days and repeat ALT/AST assessments weekly for up to 3 weeks (local blood collection may be used) or until the toxicity has resolved to <3.0 x ULN (≤ Grade 1).
	Step 2: Restart study drug at a 1 mg dose and monitor as clinically indicated. If reoccurs, discontinue study drug and monitor as clinically indicated and the participant will enter the post-treatment follow-up period.
Hematology	
 Grade 3 ANC (≤ 1.0 × 10⁹/L), unless due to underlying disease Grade 2 platelet count (50 × 10⁹/L to 	Step 1: Interrupt study drug up to 21 days until the toxicity has resolved to ≤ Grade 1 or baseline. For Grade 3 ANC, monitor at least weekly.
$<75\times10^9/L)$	Step 2: Restart study drug at same dose and monitor as clinically indicated. If reoccurs, repeat Step 1 and then restart at the 1 mg QD dose.
	Step 3: If reoccurs at 1 mg dose, discontinue study drug administration and the participant will enter the post-treatment follow-up period.

Table 9: Guidelines for Interruption and Restarting of Study Drug (Continued)

ADVERSE EVENT	ACTION TAKEN		
Hematology (continued)			
 Grade 4 ANC (< 0.5 × 10⁹/L) ≥ Grade 3 ANC with an oral temperature of at least 38.5°C OR with ≥ Grade 3 infection ≥ Grade 3 platelet count (< 50 × 10⁹/L) 	 Step 1: Interrupt study drug up to 21 days until the toxicity has resolved to ≤ Grade 1 or baseline. For ≥ Grade 3 ANC, monitor at least weekly. Step 2: Restart study drug at same dose and monitor as clinically indicated. If reoccurs, repeat Step 1 and then restart at the 1 mg QD dose. 		
	If event persists, discontinue study drug administration and the participant will enter the post-treatment follow-up period.		
Other toxicities			
Diarrhea/colitis (Grade 1)	Step 1: Treat with antimotility agents (eg, loperamide) and initiate supportive care (see Section 6.5.2). If not improved after 48 hours, treat per guidance for \geq Grade 2.		
Diarrhea/colitis (Grade 2)	Step 1: Interrupt parsaclisib or matching placebo. Perform workup for infection (including CMV, Clostridium difficile , etc) immediately. Initiate or continue supportive care (see Section 6.5.2). Monitor clinical progress closely.		
	Step 2: If improved within 48 hours and/or infection* is confirmed, restart parsaclisib/matching placebo at the same schedule and dose after resolved to ≤ Grade 1 and continue to monitor.		
	*For infectious diarrhea/colitis, follow institutional standard- of-care guidelines and restart parsaclisib/matching placebo according to clinical judgment after resolved to ≤ Grade 1. Consult with medical monitor if needed.		
	Step 3: If not improved within 48 hours and infection is ruled out, start oral steroids or consider IV steroids if participant is being given IV fluids. If no improvement with oral steroids, switch to IV steroids.		
	Step 4: When diarrhea resolves to ≤ Grade 1, continue supportive care and taper steroids according to institutional standard of care. When taper is complete (eg, no steroid or ≤ 10 mg/day prednisone or equivalent) and diarrhea is ≤ Grade 1, restart parsaclisib/matching placebo at the 1 mg QD dose with approval of the medical monitor.		
	Step 5: If Grade 2 diarrhea reoccurs, treat per guidance for diarrhea (≥ Grade 3)/noninfectious colitis.		
	Step 6: If ≥ Grade 2 diarrhea reoccurs a third time, permanently discontinue parsaclisib/matching placebo and the participant will enter the post-treatment follow-up period.		

Table 9: Guidelines for Interruption and Restarting of Study Drug (Continued)

ADVERSE EVENT	ACTION TAKEN
Other toxicities (continued)	
 Diarrhea (≥ Grade 3) Noninfectious colitis (any grade; confirmed or suspected) 	Step 1: Interrupt parsaclisib or matching placebo. Perform workup for infection (including CMV, C. difficile , etc) immediately. Initiate or continue supportive care (see Section 6.5.2). Consider colonoscopy with biopsy for diarrhea ≥ Grade 3 and/or if symptoms suggestive of colitis. Monitor clinical progress closely until resolution.
	Step 2: If infection* is ruled out, start oral steroids or consider IV steroids if participant is being given IV fluids. If no improvement with oral steroids within 48 hours, switch to IV steroids.
	*For infectious diarrhea/colitis, follow institutional standard- of-care guidelines and restart parsaclisib or matching placebo according to clinical judgment after resolved to ≤ Grade 1. Consult with medical monitor if needed.
	Step 3: When diarrhea/colitis resolves to \leq Grade 1, continue supportive care and taper steroids according to institutional standard of care. When taper is complete (eg, no steroid or \leq 10 mg/day prednisone or equivalent) and diarrhea/colitis is \leq Grade 1, restart parsaclisib or matching placebo at 1 mg QD with approval of the medical monitor. Continue to monitor. If reoccurs, discontinue study drug and the participant will enter the post-treatment follow-up period.
Pneumonitis (Grade 1)	Step 1: Interrupt parsaclisib or matching placebo until the toxicity has resolved.
	Step 2: Restart parsaclisib or matching placebo at the 1 mg QD dose. Monitor as clinically indicated.
Pneumonitis (≥ Grade 2)	Permanently discontinue parsaclisib or matching placebo and the participant will enter the post-treatment follow-up period.
Skin toxicity (eg, rash, pruritus, etc, unless otherwise specified; Grade 2-3)	Step 1: Interrupt parsaclisib or matching placebo until the toxicity has resolved to \leq Grade 1.
	Step 2: Restart parsaclisib or matching placebo at the same dose. If assessed as related to parsaclisib or matching placebo, restart at the 1 mg QD dose.
Exfoliative dermatitis (Grade 1)	Step 1: Interrupt parsaclisib or matching placebo until the toxicity has resolved.
	Step 2: Restart parsaclisib or matching placebo at the 1 mg QD dose. Monitor as clinically indicated.
Exfoliative dermatitis (≥ Grade 2)	Step 1: Interrupt parsaclisib or matching placebo until the toxicity has resolved.
	Step 2: Restart parsaclisib or matching placebo.

Table 9: Guidelines for Interruption and Restarting of Study Drug (Continued)

ADVERSE EVENT	ACTION TAKEN
Other toxicities (continued)	
CMV infection	Participants with CMV viremia without associated clinical signs of CMV infection should be carefully monitored. Consider interrupting parsaclisib or matching placebo for participants with CMV viremia and clinical signs of infection until the infection has resolved. Restart parsaclisib or matching placebo reduce to 1 mg QD dose if approved by the medical monitor.
Varicella zoster infection	Interrupt parsaclisib or matching placebo. Restart parsaclisib or matching placebo only by approval of the medical monitor.
Any Grade 1 or Grade 2 toxicity	Continue study drug administration and treat the toxicity; monitor as clinically indicated.
Any Grade 3 toxicity, if clinically significant and not manageable by	Step 1: Interrupt study drug up to 2 weeks (14 days), until toxicity resolves to ≤ Grade 1.
supportive care	Step 2: Restart study drug at same dose. If assessed as related to study drug, restart study drug at 1 mg QD dose if receiving 2.5 mg and monitor as clinically indicated.
Any recurrent Grade 3 toxicity after dose reduction	Discontinue study drug administration and the participant will enter the post-treatment follow-up period. (Exceptions require approval of sponsor.)
Any other Grade 4 toxicity	Discontinue study drug administration and the participant will enter the post-treatment follow-up period.

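### The lower-dose stop in Table 9's Grade 2 AST/ALT row requires both enzymes to be raised, so on a literal reading a one-enzyme recurrence at 1 mg is restarted, where Section 6.5.5 requires a stop

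*Protocol*

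**What the plan says.** Protocol Section 6.5.1, Table 9, opens its chemistry block with a row headed "Grade 2 AST and/or ALT is > 3.0 - 5.0 × ULN". Step 1 interrupts study drug for up to 21 days with weekly retesting. Step 2 restarts at the same dose. Three bullets follow:

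- Non-resolution: "If ALT and/or AST result(s) do not decrease to < 3.0 × ULN after 3 weeks of drug interruption, discontinue study drug administration".
- Recurrence: "If AST or ALT elevation > 3.0-5.0 × ULN reoccurs following restarting study medication administration", in which case Step 1 is repeated and drug is restarted at 1 mg QD.
- Recurrence on the lower dose: "If AST and ALT > 3.0-5.0 × ULN reoccurs on lower dose, discontinue study drug administration", with entry into post-treatment follow-up.

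Three other sections bear on the same event.

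- Section 6.5.5 defines unacceptable toxicity, not caused by the underlying disease, as requiring permanent discontinuation. Its list includes AEs that recur or persist after reduction to 1 mg QD, and also the specific stops in Table 9.
- Section 7.1.1 places unacceptable toxicity under 6.5.5, and the discontinuation criteria of Section 6.5, among the reasons for which treatment must stop.
- Section 9.1 counts an abnormal laboratory result as an AE if, among other criteria, it requires a change in study drug.

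**The concern.** One raised enzyme is enough to enter the row. One raised enzyme on recurrence is enough to force the reduction to 1 mg. The final stop, taken at its word, then needs both. A participant whose ALT alone, or AST alone, rises again at 1 mg does not meet it.

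This is an operative safety stop, and Sections 6.5.5 and 7.1.1 both rely on it. A site working from the row would interrupt and re-expose a participant whom 6.5.5 requires it to take off drug. What is at stake is participant safety and consistent conduct across sites. No estimand, analysis or data item depends on it.

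**Working it through.** No figure in the plan needs reproducing. The check is a count of wording, followed by one case taken through the rules.

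**Count.** These are the conditions in the two liver rows of Table 9 that name both enzymes:

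| # | Place | Connective |
|---|---|---|
| 1 | Grade 2 row heading | and/or |
| 2 | Grade 2 Step 1, end of interruption: "or until ALT and/or AST results are < 3.0 × ULN" | and/or |
| 3 | Grade 2 Step 2, non-resolution stop | and/or |
| 4 | Grade 2 Step 2, recurrence after restart | or |
| 5 | Grade 2 Step 2, stop on the lower dose | **and** |
| 6 | Next row's heading: "≥ Grade 3 AST and/or ALT is > 5.0 × ULN" | and/or |

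That is 4 with *and/or*, 1 with *or* and 1 with *and*: 4 + 1 + 1 = 6, so 5 of 6 accept a single enzyme. Each row's Step 1 also mentions ALT/AST assessments, but that names the tests to repeat and is not a condition.

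**Neighboring rows.** The Grade 3 or higher liver row says "Restart study drug at a 1 mg dose and monitor as clinically indicated. If reoccurs, discontinue study drug". The Grade 3 ANC and Grade 2 platelet row says "If reoccurs at 1 mg dose, discontinue study drug administration". Each stops on any recurrence of its event at 1 mg.

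**One case.** As an illustration, take ALT 4.5 × ULN with AST 1.5 × ULN, recurring at 1 mg.

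1. Row heading: 4.5 lies between 3.0 and 5.0, so the row applies on ALT alone.
2. Lower-dose stop, literal *and*: ALT qualifies. AST at 1.5 is not above 3.0 and does not. The stop is not triggered.
3. Recurrence bullet, with *or*: ALT qualifies, and the bullet is not confined to the 2.5 mg dose. It sends the participant back to Step 1 and then to a restart at 1 mg.
4. Non-resolution bullet: if ALT has not fallen below 3.0 × ULN after 3 weeks of interruption, drug is stopped. If it has fallen, the row restarts drug at 1 mg.
5. Section 6.5.5: the recurrence requires a change in study drug (step 3), so it is an AE under 9.1. It has recurred after reduction to 1 mg. If the underlying disease did not cause it, permanent discontinuation is required whether or not ALT later falls.

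The two rules therefore differ for a one-enzyme recurrence at 1 mg that resolves within 3 weeks of interruption: the row restarts and 6.5.5 stops. With *and/or* in condition 5, step 2 becomes a stop and agrees with step 5.

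**The case against.** The strongest reply is that the controlling rule is already in the protocol. Section 6.5.5 has no two-enzyme condition, and 7.1.1 makes it mandatory. Section 6.5.1 calls the dose reduction rules guidelines and asks that safety concerns go to the sponsor immediately. It also recommends consulting the medical monitor before interrupting drug, allows permanent discontinuation on any recurrence after restart, and expects sponsor contact before a restart after more than 7 days' delay. All of this stands and limits the risk. It does not cure the text. The row points to a restart where 6.5.5 requires a stop, and someone has to notice. The guideline status is also only a partial answer, because 6.5.5 and 7.1.1 both draw on the stops in Table 9.

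A second reply is that *and* may be deliberate, to tolerate AST rises driven by hemolysis. That is unlikely. It would also spare an isolated ALT rise, whereas the hemolysis exception at screening (Section 5.2, Table 7) covers AST only. Where the authors wanted an exception for disease, as for AST in Table 7 and Grade 3 ANC in Table 9, they wrote it out.

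A third reply is that the count is weak support. One of the five consistent conditions, the end of interruption in Step 1, is itself loose: literally, either enzyme below 3.0 × ULN ends the interruption. That is fair. The count shows inconsistent wording and does not measure risk.

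A reader might infer that the row says nothing about a one-enzyme recurrence at 1 mg, or can never stop it. The text does not support either. The recurrence bullet covers the case, and the non-resolution bullet stops a rise that persists.

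**Conclusion.** The row is wrong as written, and the point is minor; it is probably a drafting slip. One of six AST/ALT conditions uses *and*, and it is the stop at the reduced dose. On a literal reading, the row directs a one-enzyme recurrence at 1 mg to interruption and restart, in conflict with the mandatory stop in 6.5.5.

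The conclusion rests on three assumptions: that the bullets are read literally, that the recurrence counts as an AE under 9.1, and that it is not caused by the underlying disease.

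A reader might go further and infer that the protocol leaves such participants without any stopping rule. It does not, because 6.5.5 supplies one.

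The documents give no rate for these events, so no probability is offered. The reach is small: SAP Section 1 reports 13 participants randomized, and Protocol Amendment 2 closed enrollment. No efficacy or safety analysis changes.

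**What to change.** In the third bullet of the Grade 2 AST/ALT row, replace *and* between AST and ALT with *and/or*. Leave the rest of the bullet as it is, including entry into post-treatment follow-up.

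Add no hemolysis exception to this bullet. Section 6.5.5 already limits its mandatory stop to toxicity not caused by the underlying disease. The Table 7 wording is a screening criterion. Placed in one bullet, it would leave the heading, Step 1 and the non-resolution stop unqualified, and it would turn a wording correction into a substantive change to a stopping rule.

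The cost is one connective, issued as a protocol clarification or carried with another amendment. Section 11.1 requires health authority and IRB/IEC approval for amendments, so this does not justify one of its own. Visits, data collection and analysis are unchanged.
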